7.4.2. Discontinuations

The need to permanently discontinue doxorubicin and/or ifosfamide due to drug-related toxicity should be done according to local standard of care and labels. Criteria for olaratumab discontinuation are discussed in the olaratumab dose modification section (7.4.3.1) and in the olaratumab infusion-related reaction section (7.8.1). The need to permanently discontinue doxorubicin, ifosfamide and mesna due to drug-related toxicity will result in the permanent discontinuation of all study drugs in the doxorubicin, ifosfamide and mesna regimen.

Patients whose disease has not progressed at the time of doxorubicin, ifosfamide and mesna discontinuation will receive olaratumab as monotherapy until there is evidence of disease progression, death, intolerable toxicity, or other withdrawal criteria are met (Section 8). These patients will continue study assessments as outlined in Table JGDR.2. Patients who undergo surgical tumor resection following study treatment are not eligible to receive olaratumab as monotherapy.

Patients who exhibit disease progression at the time of doxorubicin, ifosfamide and mesna discontinuation will receive post-treatment follow-up assessments as outlined in Table JGDR.3.

7.4.3. Dose Modifications

Any patient who requires a dose reduction for drug-related toxicity will continue to receive the reduced dose for the remainder of the study.

General guidelines for dose modifications are provided below. Sections 7.4.3.2 and 7.4.3.3 outline guidelines for dose modifications of doxorubicin and ifosfamide, respectively; variations from these guidelines may be allowed according to local standard of care and labels.

7.4.3.1. Olaratumab Dose Modifications

A one-time reduction in the dose of olaratumab will be permitted if the doses of doxorubicin and ifosfamide have been previously reduced once for toxicity, and the same or similar toxicity has recurred despite reduction of doxorubicin, ifosfamide and mesna, and the toxicity is deemed potentially related to the addition of olaratumab in combination with doxorubicin, ifosfamide and mesna. In this scenario, an olaratumab dose reduction should occur in conjunction with a second reduction in the doxorubicin and ifosfamide doses according to the guidance outlined in Sections 7.4.3.2 and 7.4.3.3.

A second reduction in the olaratumab dose will not be permitted during treatment with combination therapy of olaratumab plus doxorubicin and ifosfamide.

Patients who have not progressed on study will receive olaratumab as monotherapy following discontinuation of the combination therapy until there is evidence of disease progression, death, intolerable toxicity, or other withdrawal criteria are met. Patients receiving olaratumab as monotherapy will have assessments performed as per Table JGDR.2.

Patients who have a dose reduction of olaratumab during the combination therapy portion and then proceeding to receive olaratumab monotherapy after discontinuation of doxorubicin and ifosfamide.

ifosfamide combination may have their dose of olaratumab re-escalated to the original dose level at the investigator's discretion.

7.4.3.1.1. Hematologic Toxicity

Table JGDR.8 shows olaratumab dose modifications that should be made for hematologic toxicities judged as potentially related to olaratumab in combination with doxorubicin, ifosfamide and mesna, and that have recurred or failed to improve/resolve despite 1 reduction in doxorubicin and ifosfamide doses. These guidelines should be used for olaratumab dosing, when given in combination with doxorubicin and ifosfamide.

Table JGDR.8. General Guidelines for Olaratumab Dose Modification due to Hematologic Toxicities

Toxicity	Required-Dose Modification
Neutropenia	
ANC Grades 1-3	No dose modification required
ANC <500 cells/ μ L (Grade \geq 4)	No treatment administered; treatment cycle delayed
At re-treatment: If \geq Grade 3 neutropenic fever/infection has occurred and 1 reduction in doxorubicin, ifosfamide and mesna doses has already occurred	Withhold dose until ANC is \geq 1500 cells/ μ L; 
 • 15-mg/kg Dose Level: Reduce dose to 12 mg/kg • 20-mg/kg Loading Dose Cycle Level: Reduce dose to 15 mg/kg
If Grade 4 neutropenia lasting \geq 1 week has occurred and 1 reduction in doxorubicin, ifosfamide and mesna doses has already occurred	Withhold dose until ANC is \geq 1500 cells/ μ L; 
 • 15-mg/kg Dose Level: Reduce dose to 12 mg/kg • 20-mg/kg Loading Dose Cycle Level: Reduce dose to 15 mg/kg
Grade 4 ANC without fever/infection lasting \leq 1 week	Administer next olaratumab at full dose, at investigator's discretion
After 1 reduction of olaratumab and 2 reductions of doxorubicin, ifosfamide and mesna, recurrence of either: 1) \geq Grade 3 neutropenic fever/infection 2) Grade 4 neutropenia lasting \geq 1 week	Discontinue combination therapy (olaratumab + doxorubicin/ifosfamide/mesna). Patients who have not progressed will receive olaratumab as monotherapy until there is evidence of disease progression, death, intolerable toxicity, or other withdrawal criteria are met.

Abbreviation: ANC = absolute neutrophil count.

Omitting the Day 8 dose of olaratumab based on ANC and platelet counts judged as potentially related to olaratumab in combination with doxorubicin, ifosfamide, and mesna is permissible as shown in Table JGDR.9.

7.4.3.2. Doxorubicin Dose Modifications

Dose modifications of doxorubicin will follow the guidelines outlined below and may be adjusted according to local standard of care and label. Two reductions in doxorubicin dose will be permitted during the study according to the guidance outlined in Sections 7.4.3.5 and 7.4.3.6. If

~~a third dose reduction is necessary, the patient will be discontinued from the combination therapy (olaratumab + doxorubicin/ifosfamide/mesna) and will be followed as outlined in Section 7.4.2.~~

7.4.3.2.1. Hematologic Toxicity

Doxorubicin will not be administered after the initial dose if the patient's ANC is <1500 cells/ μ L or if the platelet count is $<100,000$ cells/ μ L. When necessary, the next treatment cycle should be delayed until the ANC is ≥1500 cells/ μ L and the platelet count is $\geq100,000$ cells/ μ L and any nonhematologic toxicities have resolved. For patients who experience \geq Grade 3 neutropenic fever or infection or Grade 4 neutropenia without fever lasting more than 1 week, doxorubicin should be reduced to 75% of the starting dose (that is, to approximately 60 mg/m^2). If a patient experiences a second incidence of neutropenic fever/infection or has another episode of Grade 4 neutropenia lasting >1 week, then a second dose reduction to 45 mg/m^2 ~~should occur~~ will be necessary.

7.4.3.3. Ifosfamide Toxicities and Dose Modifications

Dose modifications of ifosfamide will follow the guidelines outlined below and may be adjusted according to local standard of care and label. Two reductions in ifosfamide dose for toxicity will be permitted during the study. If a third dose reduction is necessary, the patient will be discontinued from the combination therapy (olaratumab + doxorubicin/ifosfamide/mesna) and followed as outlined in Section 7.4.2.

General guidelines for ifosfamide dose modification are shown in Table JGDR.12. Dose modifications of ifosfamide due to hepatic impairment are shown in Table JGDR.13.

7.4.3.3.2. Ifosfamide-Associated Urotoxic Effects

The incidence of urotoxic effects without an uroprotector can be up to 40% and is dose dependent; coadministration of mesna and adequate hydration are mandatory in this study. Patients may present with hematuria, symptomatic cystitis, or bladder fibrosis. Past or concomitant radiation of the bladder or busulfan treatment may increase the risk of hemorrhagic cystitis. Several methods of treatment for established hematuria have been described: bladder irrigation with water or normal saline, intravesical instillation of astringents (alum, silver nitrate), systemic administration of antifibrinolitics (aminocaproic acid, tranexamic acid), cystoscopy to evacuate the bladder of clots, continuous bladder irrigation and intravesical prostaglandins. For severe or refractory hematuria, intravesical formalin, phenol, or prostaglandin has been used with or without surgical intervention (electrocautery, cryosurgery, diversion of urine flow, hypogastric artery ligation, or cystectomy). ~~Ifosfamide should be discontinued or dose reduced~~ Discontinuation or dose reduction of ifosfamide should follow local standard of care and label for patients with macroscopic hematuria.

7.4.3.3.3. Ifosfamide-Associated Proximal Tubular Damage

Glomerular, proximal, or distal tubular impairment may all occur, often in combination and may progress even after ifosfamide has been discontinued. Proximal tubular damage often presents as Fanconi syndrome with low serum bicarbonate, proteinuria, glucosuria, aminoaciduria and hypochloremic metabolic acidosis. Risk factors for the development of nephrotoxicity include preexisting renal impairment, concurrent use of nephrotoxic drugs, reduced renal reserve (unilateral nephrectomy), hydronephrosis and total cumulative dose. Renal impairment may increase the risk of myelosuppression and possibly, cardiotoxicity. Mesna does not appear to be protective against the proximal tubular abnormalities induced by ifosfamide. Dose modifications guidelines of ifosfamide due to renal impairment are shown in Table JGDR.14.

7.7. Treatment Compliance

The study medication will be administered only at the investigational sites by the authorized study site personnel. As a result, treatment compliance is ensured.

7.8.6. Other Concomitant Therapies

No other chemotherapy, radiotherapy, immunotherapy, cancer-related hormone therapy, or experimental drugs will be permitted while the patients are on this study. An exception will be made for:

- prostate cancer patients continuing GnRH agonist therapy or breast cancer patients continuing anti-estrogen therapy (for example, an aromatase inhibitor) as long as those therapies have been installed for at least 3 months and are known to have been well tolerated
- bisphosphonate osteoclast inhibitors (for example, zoledronic acid or pamidronate) for treatment of bone metastases will be permitted while patients are on study treatment. The osteoclast inhibitor denosumab is also allowed. Denosumab is a monoclonal antibody and is associated with a risk of hypersensitivity reactions. Therefore, denosumab should not be administered within 3 days of olaratumab administration.
- palliative local treatment (for example, radiotherapy of <14 calendar days) in Cycles 2 and beyond following discussions between the investigators and the sponsor (for example, for pain control of a solitary [non-skull] skeletal metastasis) and written approval by the sponsor, as long as the patient has not developed another reason for study discontinuation.

9.1. Efficacy Assessments

9.1.1. Secondary Efficacy Assessments

Tumor assessments will ...

The method of tumor assessment used at baseline must be used consistently throughout the study. Radiological scan imaging of the chest thorax, abdomen and pelvis and other areas, as clinically indicated, is required.

See Section 10.3.1 for definitions of the efficacy endpoints.

10. Statistical Considerations

10.1. Sample Size Determination

The primary objective is to ...

Before enrolling the full 15 patients at a given dose level, the study design requires that an initial group of 6 will be enrolled and evaluated for DLTs. If 6 or more patients with DLTs are observed in the first 6 patients, enrollment at the current dose level will be stopped and appropriate dose de-escalation (or trial halt) will occur. Similarly, if 6 or more patients with DLTs are observed in the first 9 patients, enrollment at the current dose level will be stopped and appropriate dose de-escalation (or trial halt) will occur.

Appendix 3. Clinical Laboratory Tests

Clinical Laboratory Tests

Hematology - local and central laboratory^a

Leukocytes (WBC)	Erythrocytes (RBC)
Neutrophils ^b	Hemoglobin (HGB)
Lymphocytes	Hematocrit (HCT)
Monocytes	Mean corpuscular volume (MCV)
Eosinophils	Mean corpuscular hemoglobin concentration (MCHC)
Basophils	Platelets (PLT)

Coagulation - local laboratory

Activated partial thromboplastin time (aPTT) or partial thromboplastin time (PTT)
International normalized ratio (INR) or prothrombin time (PT)

Clinical Chemistry - local and central laboratory^a

Serum Concentrations of:

Alanine aminotransferase (ALT)	Cholesterol
Albumin	Creatinine
Alkaline phosphatase	Glucose, random
Aspartate aminotransferase (AST)	Magnesium
Bilirubin, direct	Phosphorous
Bilirubin, total	Potassium
Blood urea nitrogen (BUN) or blood urea	Sodium
Calcium	Uric acid

Urinalysis - local laboratory

Blood	Protein
Glucose	Specific gravity
Ketones	Urine leukocyte esterase
pH	

Pregnancy Test (for female patients of childbearing potential) - local laboratory

Serum pregnancy test (screening)

Serum or Urine pregnancy test (on study)

Confirmation of Menopause (for female patients of menopausal age) – local laboratory

Follicle-stimulating hormone (FSH)^c

Abbreviation: CRF = case report form.

a Treatment decisions will be based on local laboratory results.

b Neutrophils reported using automated differential hematology instruments include both segmented and band forms. When a manual differential is needed to report the neutrophils, the segmented and band forms should be added together and recorded on the CRF, unless the CRF specifically provides an entry field for bands.

c To be performed at screening only when needed to confirm post-menopausal status; applicable for women who have experienced spontaneous amenorrhea for 6 to 12 months.

Appendix 4. Pharmacokinetic, Biomarker, Pharmacogenetics and Immunogenicity Sampling Schedules

It is essential that the exact infusion start and stop times (actual clock readings) are recorded. The exact time of collection of each venous blood sample will be based on the clock used to record infusion times. It is essential that the PK blood samples not be drawn from the same site as the drug infusion.

Pharmacokinetic, Biomarker, Pharmacogenetic and Immunogenicity Sampling Schedule

Cycle	Day	Dosing	Sampling Time ^a	PK Sampling			Biomarker Sampling		PGx	IG ^{e,f}
				Olara PK ^{b,f}	Dox PK ^{c,l}	Ifos PK ^{d,l}	Plasma	Tumor Tissue ^g		
Baseline	-							X (mandatory) ^g		
1	1		≤60 min pre-olara	X ^h			X		X ⁱ	X
		Olara (1 hr)								
			≤5 min post-olara	X						
		Obs (1 hr)								
			60±10 min post-olara	X						
		Dox (<1 hr) ^j								
			≤5 min post-dox		X ^j					
	2	Ifos (3 hr)								
			≤5 min post-ifos	X			X			
		Dox (<1 hr)								
2	3	Ifos (3 hr)								
			≤5 min post-ifos	X			X			
		Dox (<1 hr) ^j								
	4		≤5 min post-dox		X ^j					
		Ifos (3 hr)								
			≤5 min post-ifos				X			
	8	Ifos (3 hr)								
			≤5 min post-ifos	X			X			
			≤60 min pre-olara	X ^h				X		X
		Olara (1 hr)								
			≤5 min post-olara	X						
		Obs (1 hr)								
			60±10 min post-olara	X						
2	1		4±0.5 hr post-olara	X						
		10	48±3 hr post-olara	X						
	8	15	Anytime	X						
			≤60 min pre-olara	X ^h				X		X
		Olara (1 hr)								
			≤5 min post-olara	X						

		≤60 min pre-olara	X ^h			X			X
3	1	Olara (1 hr)							
		≤5 min post-olara	X						
		Dox (<1 hr) ⁱ							
		≤5 min post-dox	X	X ^j					
		Ifos (3 hr)							
		≤5 min post-ifos	X		X				
	2	Dox (<1 hr)							
		Ifos (3 hr)							
		≤5 min post-ifos	X ^k		X				
	3	Dox (<1 hr) ⁱ							
		≤5 min post-dox		X ^j					
		Ifos (3 hr)							
	4	≤5 min post-ifos			X				
		Ifos (3 hr)							
		≤5 min post-ifos	X ^k		X				
	8	≤60 min pre-olara	X ^h						
		Olara (1 hr)							
		≤5 min post-olara	X						
		60±10 min post-olara	X						
	10	4±0.5 hr post-olara	X						
		48±3 hr post-olara	X						
		Anytime	X						
4	1	≤60 min pre-olara	X ^h						
5 and then every other cycle	1	≤60 min pre-olara	X ^h						X
Visit 801		Anytime	X			X	X (optional; for patients who undergo surgical tumor resection subsequent to study treatment)		X

Abbreviations: C = cycle; D = day; dox = doxorubicin; hr = hour; ifos = ifosfamide; IG = immunogenicity; min = minute; IRR = infusion-related reaction; obs = observation; olara = olaratumab; PGx = pharmacogenetics; PK = pharmacokinetics.

a Post-infusion is defined as after the completion of the infusion.

b Samples of approximately 3 mL of whole blood will be drawn without anticoagulant for measurement of olaratumab in serum.

- c Samples of approximately 2 mL of whole blood will be drawn into plastic tubes with anticoagulant for measurement of ifosfamide in plasma.
- d Samples of approximately 3 mL of whole blood will be drawn into plastic tubes with anticoagulant for measurement of doxorubicin in plasma.
- e For the immunogenicity assay, approximately 5 mL of whole blood will be drawn into a serum separator tube without anticoagulant to generate serum samples.
- f If a patient experiences an IRR to olaratumab, blood samples for immunogenicity and PK analysis will be taken at the following time points: (1) as soon as possible after the onset of the IRR, (2) at the resolution of the IRR and (3) 30 days (± 3 days) after the IRR.
- g Patients must have sufficient available material from an archived formalin-fixed paraffin-embedded tumor tissue. If such tissue is not available, a newly obtained core or excisional biopsy of a tumor lesion must be performed.
- h Pretreatment olaratumab PK samples may be collected up to 60 minutes prior to the olaratumab infusion and must be prior to administering any premedication. Pretreatment samples may be collected any time during the day of the clinical visit, prior to the start of the olaratumab infusion and must be taken prior to administering any premedication.
- i It is highly recommended to draw the PGx sample prior to the first dose of study drug (C1D1); however, it can be collected at a later time point, if necessary.
- j If doxorubicin is administered as a 24 hour infusion, the doxorubicin PK sample should be collected at the same time as the ifosfamide PK sample (that is, approximately 3 to 4 hours after the start of the doxorubicin infusion).
- k For patients who have discontinued doxorubicin/ifosfamide early, these samples may be omitted if there is no other reason for the patient to visit the clinic.
- l Should a patient discontinue doxorubicin or ifosfamide, all subsequent PK samples for the corresponding chemotherapeutic agent can be omitted.

Leo Document ID = 162b3c09-f0fb-440a-956f-85d421fbbebd

Statistical Analysis Plan I5B-MC-JGDR

A Phase 1b Study of Olaratumab, Doxorubicin and Ifosfamide in the Treatment of Patients With Advanced or Metastatic Soft Tissue Sarcoma

NCT03283696

Approval Date: 28-Aug-2017

1. Statistical Analysis Plan I5B-MC-JGDR: A Phase 1b Study of Olaratumab, Doxorubicin and Ifosfamide in the Treatment of Patients with Advanced or Metastatic Soft Tissue Sarcoma

Confidential Information

The information contained in this document is confidential and the information contained within it may not be reproduced or otherwise disseminated without the approval of Eli Lilly and Company or its subsidiaries.

Note to Regulatory Authorities: this document may contain protected personal data and/or commercially confidential information exempt from public disclosure. Eli Lilly and Company requests consultation regarding release/redaction prior to any public release. In the United States, this document is subject to Freedom of Information Act (FOIA) Exemption 4 and may not be reproduced or otherwise disseminated without the written approval of Eli Lilly and Company or its subsidiaries..

Olaratumab (LY3012207) Soft Tissue Sarcoma

Study JGDR is a Phase 1b, multicenter, nonrandomized, open-label study of intravenous olaratumab (15 mg/kg on Days 1 and 8 or 20-mg/kg loading dose on Days 1 and 8 in Cycle 1 followed by 15 mg/kg on Days 1 and 8 of subsequent cycles) combined with doxorubicin (25 mg/m² on Days 1, 2, 3), ifosfamide (2.5 g/m² on Days 1, 2, 3, 4) and mesna (≥60% of ifosfamide dose on Days 1, 2, 3, 4) in 21-day cycles in the treatment of patients with advanced or metastatic soft tissue sarcoma. Patients will receive combination treatment for a maximum of 6 cycles followed by olaratumab as monotherapy until there is evidence of disease progression, death, intolerable toxicity, or other withdrawal criteria are met.

Eli Lilly and Company
Indianapolis, Indiana USA 46285
Protocol I5B-MC-JGDR
Phase 1b

Statistical Analysis Plan electronically signed and approved by Lilly on date provided below.

Approval Date: 28-Aug-2017 GMT

2. Table of Contents

Section	Page
1. Statistical Analysis Plan I5B-MC-JGDR: A Phase 1b Study of Olaratumab, Doxorubicin and Ifosfamide in the Treatment of Patients with Advanced or Metastatic Soft Tissue Sarcoma	1
2. Table of Contents	2
3. Revision History	6
4. Study Objectives	7
4.1. Primary Objective	7
4.2. Secondary Objectives	7
4.3. Exploratory Objectives	7
5. A Priori Statistical Methods	8

4.1. Primary Objective

The primary objective is to characterize the safety profile of olaratumab when given in combination with doxorubicin, ifosfamide and mesna and to determine the dosing regimen appropriate for a future Phase 2 study.

4.2. Secondary Objectives

The secondary objectives are:

- to evaluate the pharmacokinetics (PK) of olaratumab when combined with doxorubicin, ifosfamide and mesna
- to evaluate the immunogenicity of olaratumab when combined with doxorubicin, ifosfamide and mesna
- to document any antitumor activity of olaratumab when combined with doxorubicin, ifosfamide and mesna

4.3. Exploratory Objectives

The primary objective is to explore biomarkers related to, but not limited to tumor microenvironment, immune cells/immune functioning, mechanism of action of study drugs, platelet-derived growth factor receptor (PDGF), cancer-related pathways and disease state, and their association with demographics, disease state and clinical outcomes.

5. A Priori Statistical Methods

5.1. Sample Size Determination

The sample size determination is described in Protocol I5B-MC-JGDR (JGDR), Section 10.1.

5.2. General Considerations

5.2.1. Populations

The following population will be defined for this study:

Safety population: All enrolled patients who receive any quantity of study treatment, regardless of their eligibility for the study, will be included in the safety analysis. Safety evaluation will be performed based on the actual initial therapy a patient has received. Efficacy analysis will be performed on the safety population unless otherwise specified.

DLT-evaluable population: The DLT-evaluable population will include all enrolled patients who complete Cycle 1 or discontinue due to a DLT prior to completing Cycle 1.

5.2.2. Definitions and Conventions

The **baseline value** is the last non-missing value observed prior to the first dose of study treatment.

The **study day** will be calculated as: assessment date – first dose date + 1 day if the assessment is done on or after the first dose day. If the assessment is done prior to the first dose day, study day will be calculated as assessment date – first dose date.

Date of first dose is defined as study Day 1.

One month is defined as 365/12 days.

Unless otherwise noted, **summaries of continuous variables** will include mean, median, standard deviation, minimum, and maximum. When appropriate, lower and upper quartiles will also be presented.

Unless otherwise noted, summaries of **categorical variables** will include the frequency and percentage (relative to the population being analyzed) of each category.

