AE collection	X						X		Collect continuously throughout the treatment period; CTCAE Version 4.0.
ECOG performance status	X					X			
Radiologic imaging and measurement of palpable or visible lesions	X						X		
 • Perform according to RECIST 1.1, by the same method used at baseline, q 6 weeks (-7 days) from the start of treatment until radiographic disease progression, death, or study completion, whichever occurs first. • Perform as scheduled, even if study treatment is delayed or omitted.
ECG	X					X			
 • Perform local 12-lead ECG on Day 1 of Cycle 1 through Cycle 6. • Perform local 12-lead ECG on Day 1 of Cycle 7 and approximately 6 months (\pm14 days) and 12 months (\pm14 days) after discontinuation of doxorubicin and ifosfamide treatment
Echocardiogram and/or MUGA scan	X C4 and C6						X		
 • Perform at the end of C4 and C6; perform additional evaluations in the setting of cardiac symptoms and/or at the discretion of the investigator. • For patients receiving olaratumab as monotherapy following discontinuation of combination therapy, perform approximately 6 months (\pm14 days) and 12 months (\pm14 days) after discontinuation of doxorubicin and ifosfamide treatment.
Hematology	X				X	X	X	X	\leq 3 days prior to administration of study treatment on D1 and \leq 1 day prior to administration of study treatment on D8, unless more frequent assessment is clinically indicated. Day 15 labs may be drawn within \pm 1 day of Day 15. See Appendix 3 . To be performed locally for patient management and centrally for analysis purposes.

Day within Cycle Procedure	Cycles 1-6 (olaratumab + doxorubicin + ifosfamide; (Cycle = 21 days)						Cycles 7-N Olaratumab Monotherapy ^a (Cycle = 21 days)		Instructions
	1	2	3	4	8	15	1	8	
Coagulation	X						X		≤3 days prior to administration of study treatment on D1, unless more frequent assessment is clinically indicated. For patients receiving olaratumab as monotherapy following combination therapy discontinuation, perform on D1 of every other cycle. See Appendix 3 . To be performed locally.

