[6] Have a performance status of 0 to 1 on the Eastern Cooperative Oncology Group scale.

[7] Have received no prior lines of systemic therapy (adjuvant or neo-adjuvant treatment will not be counted as a prior line) and are suitable to receive doxorubicin, ifosfamide and mesna. All previous anticancer treatments must have completed ≥ 3 weeks (21 days) prior to the first dose of study treatment.

[8] Have left ventricular ejection fraction (LVEF) $\geq 50\%$ assessed within 28 days prior to enrollment.

[9] Have resolution of AEs, with the exception of alopecia, and of all clinically significant toxic effects of prior locoregional therapy, surgery or radiotherapy to \leq Grade 1, by National Cancer Institute-Common Terminology Criteria for Adverse Events (NCI-CTCAE) Version 4.0.

[10] Have sufficient available material from archived formalin-fixed paraffin-embedded tumor tissue for biomarker-related studies. If such tissue is not available, a newly obtained core or excisional biopsy of a tumor lesion must be performed. Patients for whom it is inadvisable to undergo a new biopsy in the opinion of the investigator (for example, due to technically challenging tumor location) may be enrolled, after prior discussion with the Lilly clinical research physician (CRP). Refer to Section 9.7.2 regarding tissue collection requirements.

[11] Are reliable and willing to make themselves available for the duration of the study and are willing to follow study procedures.

[12] If male, must be sterile or agree to use an *effective method of contraception* or a *highly effective method of contraception* during the study and for at least:

- 3 months following the last dose of olaratumab
- 6 months following the last dose of doxorubicin or ifosfamide

Refer to [Appendix 1](#) for definitions of *effective method of contraception* and *highly effective method of contraception*.

[13] If female and of child-bearing potential, must:

- a. have a negative serum pregnancy test within 7 days prior to the first dose of study treatment, and

- b. agree to use a *highly effective method of contraception* during the study and for at least 3 months following the last dose of olaratumab and 6 months following the last dose of doxorubicin or ifosfamide.

Refer to [Appendix 1](#) for the definitions of *highly effective method of contraception* and *effective method of contraception*.

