5.3. Handling of Dropouts or Missing Data

With the exception of dates, missing data will not be imputed. The method of imputation for any dates that are imputed is described in the relevant sections.

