5.8. Safety Analyses

All safety analyses will be performed on the safety population within each cohort. Safety analyses will also be performed combining patients treated within the dose confirmatory phase with patients treated at the same dose level within the dose finding phase.

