5.8.8. Electrocardiograms, Echocardiogram / Multiple Gated Acquisition Scan

Electrocardiograms (ECG) findings that are considered to be a medical history condition or an AE will be summarized and listed.

Left ventricular ejection fraction (LVEF) results will be summarized by scheduled time point.

Changes in LVEF will also be summarized including percentage of patients with LVEF decrease of $\geq 10\%$ and below the lower limit of normal, or an absolute decrease of 20%, or an absolute LVEF decreases to or below 40%.

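### The percentage of patients with an LVEF decrease is taken over all treated patients, including any never scanned after baseline, so it is a lower bound and can understate LVEF decline

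*SAP*

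**What the plan says.** **Denominator.** Unless otherwise noted, SAP 5.2.2 summarises categorical variables by the "frequency and percentage (relative to the population being analyzed) of each category". SAP 5.8 states: "All safety analyses will be performed on the safety population within each cohort". SAP 5.2.1 defines that population broadly: "All enrolled patients who receive any quantity of study treatment, regardless of their eligibility for the study, will be included in the safety analysis". No scan after baseline is needed to belong to it.

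**The summary in question.** SAP 5.8.8 reads: "Changes in LVEF will also be summarized including percentage of patients with LVEF decrease of", followed by three limits that match those for stopping doxorubicin in Protocol 7.4.3.2.3. It gives no denominator and does not mention patients without a later scan. On missing data generally, SAP 5.3 says: "With the exception of dates, missing data will not be imputed".

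**When scans happen.** Baseline LVEF is an eligibility item in Protocol 6.1, "assessed within 28 days prior to enrollment". During combination treatment the instruction in Protocol Table JGDR.2 is: "Perform at the end of C4 and C6; perform additional evaluations in the setting of cardiac symptoms and/or at the discretion of the investigator". Tables JGDR.2 and JGDR.3 add scans at about 6 and 12 months after doxorubicin and ifosfamide end. Table JGDR.3 has no echocardiogram/MUGA mark at Visit 801, and it lets these scans stop once another anticancer therapy begins. Protocol 7.9.1 ends long-term follow-up when continued access opens, and the continued access schedule (Table JGDR.4) has no echocardiogram row.

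**The concern.** A treated patient with no LVEF value after baseline cannot meet any of the three limits. Under the default denominator that patient still counts in the base of the percentage, with the same effect as a patient scanned and found stable. The SAP bars imputation, yet the resulting figure cannot separate no decline from not looked at.

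The primary objective is to characterise safety and choose a regimen, and cardiac dysfunction is an adverse event of special interest. If the scanned fraction differs between cohorts, for instance because one has more early discontinuation, the percentages also differ for a reason unrelated to cardiac effect.

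The SAP is more careful elsewhere. DLTs have their own evaluable population (5.2.1), best overall response has a not-evaluable category with a stated denominator (5.9.1), and the registry tables adjust the number at risk (5.14). The LVEF summary has nothing comparable.

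**Working it through.** The documents state no LVEF-decline rate, scan-completion rate or dropout rate, so there is no plan figure on this point to reproduce. The check has two parts.

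**1. Can a treated patient go unscanned after baseline?**

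- Stopping all treatment before the end of Cycle 4: no scheduled on-treatment scan and none at Visit 801. The next is due at about 6 months and may lapse.
- Stopping chemotherapy early and continuing olaratumab: Table JGDR.2, footnote a, moves the patient to the monotherapy schedule from the next cycle. The next scheduled scan is again at about 6 months.
- Study end: Protocol 5.3 completes the study 30 days after the Dose Confirmation Phase finishes combination therapy. Without delays this is 6 × 21 + 30 = 156 days from the last patient's first dose. For a patient starting at the same time who stops at the end of Cycle 1, the 6-month scan falls near day 21 + 6 × 365/12 = 203.5, after study completion.

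Unscanned patients are therefore foreseeable. Their number is not known.

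**2. What does the default denominator do?**

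Let N be treated patients, U those with no post-baseline LVEF, and x the observed declines.

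- Reported percentage: x/N
- Percentage among scanned patients: x/(N − U)
- Ratio of the first to the second: (N − U)/N
- Upper bound for all treated patients: (x + U)/N

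N = 30 is the approximate number planned on the recommended regimen (Protocol 5.2). The values x = 4 and U = 0, 6 and 10 are assumptions.

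| U (assumed) | Reported x/N | Among scanned | Ratio | Upper bound |
|---|---|---|---|---|
| 0 | 4/30 = 13.3% | 4/30 = 13.3% | 1.00 | 4/30 = 13.3% |
| 6 | 4/30 = 13.3% | 4/24 = 16.7% | 24/30 = 0.80 | 10/30 = 33.3% |
| 10 | 4/30 = 13.3% | 4/20 = 20.0% | 20/30 = 0.67 | 14/30 = 46.7% |

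The reported figure is the same in every row, and a reader could not tell which row applies.

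The true share among all treated patients depends on the unscanned. If their decline rate is q times that of the scanned, it is (x + q × U × x/(N − U))/N. With U = 6:

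- q = 0: 4/30 = 13.3%
- q = 0.5: (4 + 0.5)/30 = 15.0%
- q = 1: (4 + 1)/30 = 16.7%

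At q = 0 the reported figure is right and the scanned-only figure is too high. At q = 1 the scanned-only figure is right.

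For two cohorts of 15 (assumed counts), 3 declines with everyone scanned give 3/15 = 20.0%. Two declines with 5 unscanned give a reported 2/15 = 13.3%, although the rate among the scanned is also 2/10 = 20.0%.

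**The case against.** The strongest reply is that nothing here shows harm to be understated, and that stands. A reader might infer that doxorubicin cardiotoxicity is understated as a matter of fact. The documents give no count of unscanned patients, and x/N is too low only if at least one of them had an undetected decline.

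A second reply also stands: the scanned-only rate is not automatically the right benchmark. Protocol 7.4.3.2.3 says the cardiac risk rises with cumulative doxorubicin exposure, so patients who leave before the end of Cycle 4 have had less of it. Extra scans are prompted by cardiac symptoms, which tilts scanning towards suspected cases. Both can make the scanned-only rate overstate the rate among all treated patients.

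Third, the SAP does not say outright that a missing value means no decline, and a missing category is not excluded. This helps only partly. A missing row would disclose the count, but the decline percentage would still be x/N.

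Fourth, cardiac dysfunction is also tabulated as an adverse event of special interest, with ejection fraction decrease among its terms, and LVEF is summarised by scheduled time point. These are useful, but a symptomless fall in an unscanned patient is missed there too. SAP 5.2.2 also does not list a patient count among the statistics for continuous variables.

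Finally, the summaries are descriptive and the formal dose thresholds rest on Cycle 1 DLTs. A claim that cohorts cannot be compared at all would go too far. Nor does the argument extend to the laboratory tables in SAP 5.8.6: hematology and chemistry are drawn on Days 1, 8 and 15 of Cycles 1 to 6, so there is no comparable late first assessment.

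**Conclusion.** The point holds as a reporting weakness. Read together, SAP 5.2.2, 5.2.1 and 5.8 make all treated patients the denominator for the LVEF-decline percentage in 5.8.8. Patients without a post-baseline scan can only dilute it, so it is a lower bound (setting aside measurement error) and can understate LVEF decline.

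The size cannot be given from the documents. The reported rate is the scanned-patient rate times the scanned fraction: with 30 treated, 0.80 times if 6 are unscanned and 0.67 times if 10 are, both assumed counts. If everyone is scanned, or if no unscanned patient declined, nothing is understated. Two stronger readings are not supported: that understatement is established, and that the scanned-only percentage should replace the safety-population one.

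**What to change.** In SAP 5.8.8, report for each cohort, and for the pooled recommended-regimen group in SAP 5.8:

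- the number of patients with a baseline and at least one post-baseline LVEF;
- the percentage with a decline over that number, beside the percentage over the safety population;
- the number without a post-baseline LVEF.

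Leave SAP 5.8.6 as it is. The cost is SAP wording and a few extra table rows from data already collected, with no new scans. The added percentage will rest on a smaller denominator and look less favourable whenever there is at least one decline and someone is unscanned.
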